In order to maximise the potential benefits from prehabilitation, including improved surgical outcomes and reduced costs to the NHS, accessibility is key. Commonly, prehabilitation is delivered via face-to-face sessions in hospital or community facilities. However, the most frequently reported barriers to engagement in prehabilitation programmes are lack of time and difficulty travelling to facilities on a regular basis (Gurunathan et al., 2023, van der Velde et al., 2023, Waterland et al., 2021). In addition to presenting a barrier to patients, face-to-face interventions are accompanied by high running costs to the healthcare provider, making the economic case for their implementation challenging (Barberan-Garcia et al., 2019). Furthermore, in-person interventions are vulnerable to disruption, e.g., during the Covid-19 pandemic, with the target population of surgical patients susceptible to infection. As such, home-based interventions may provide an alternative approach. Indeed, a systematic review of prehabilitation studies identified home-based programmes as a strategy to overcome commonly-reported barriers of lack of time when scheduling prehabilitation around work, medical appointments, and practical tasks, plus lack of transport and parking (van der Velde et al., 2023).

In prior studies, it has been shown that ~70% of patients would prefer to complete prehabilitation in their home (Gurunathan et al., 2023, Waterland et al., 2021). Furthermore, patients and/or their informal carers identify a tailored approach based on individual needs and preferences, access to resources, the ability to

monitor their progress, and motivation from achieving objective progressions as facilitators to engaging in prehabilitation (van der Velde et al., 2023, Agasi-Idenburg et al., 2020). Traditional paper handouts of exercises to perform at home may not provide scope for individually-tailored, progressive, and engaging exercise prescriptions, and have been shown to be inferior to digital home-based interventions (Lambert et al., 2017). Therefore, digital home-based prehabilitation interventions may overcome issues with face-to-face and traditional home-based interventions.

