 - Major or complex surgery examples in NICE guideline NG45 'Routine preoperative tests for elective surgery' provides appropriate examples that are relevant to the patient cohort at RUH. We have extrapolated from these examples a list of surgical procedures that qualify as major or complex surgery and are carried out at the RUH. This list is not exhaustive but provides a range of procedures that are applicable for example: laparotomy, joint replacement, total abdominal hysterectomy, nephrectomy, neck dissection, parotidectomy, endoscopic resection of prostate, thyroidectomy.
- Aged ≥ 50 years

Subgroups of patients will be excluded:

- Surgery scheduled in <10 weeks
- Any relative or absolute contraindications to undertake an exercise test as described by the American College of Sports Medicine (ACSM, 2022) and the American Heart Association (Fletcher et al., 2013)
- Unsuitable to increase physical activity level as determined by Physical Activity Readiness Questionnaire (PAR-Q)
- Uncontrolled or poorly-controlled lung condition, diabetes, or seizures
- Recent (<12 months) cardiovascular events needing hospital admission
- Ongoing infection or wound making this programme hazardous for the patient
- Unable to access technology required to use the PreActiv digital platform

- Currently meeting World Health Organisation (WHO) physical activity guidelines of 75-300 minutes of moderate to vigorous intensity physical activity per week, plus twice-weekly muscle strengthening activities
- Unable to understand explanations and/or provide informed consent
- Unable to understand written or spoken English, and without ongoing access to an interpreter
- Any condition and/or behaviour that would pose undue personal risk or introduce bias into the study
- Currently enrolled in another research trial

5. Study procedures

a. Sample size

A sample size of $N = 34$ has been selected, based on the primary aim of this pilot study to determine whether progression to a full-scale study is indicated, according to predefined progression criteria. Methodology for sample size estimation in external pilot studies published by Lewis et al. (2021) has been used to inform the sample size. A traffic light system (Avery et al., 2017) has been used to define progression criteria based on two key outcome measures - adherence and retention:

	Red stop	Amber amend	Green go
Adherence	0-50%	51-74%	75-100%
Retention	0-50%	51-74%	75-100%

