Based on these progression criteria, and aiming to test the hypothesis that feasibility outcomes will not fall within the red zone (*stop*) based on the expectation of being in the green zone (*go*) with 90% power and one-sided alpha of 0.05, we need to consent $N = 34$ participants. As such, recruitment will cease once $N = 34$ participants have provided written informed consent.

b. Recruitment, screening & informed consent

Participants will be recruited from the preoperative assessment clinic at the RUH. Preoperative assessment clinic is delivered predominantly via a virtual clinic ('MyPreOp') at the RUH, whereby patients complete questionnaires and provide consent for surgery online. However, all patients awaiting major elective surgery are required to attend the RUH for a blood test as a minimum, with patients aged ≥ 65 years and/or those with systemic disease also required to attend for ECG, as per the NICE guidelines (NICE, 2016). Preoperative nurses will identify potentially eligible patients who are booked for a blood test and/or ECG appointment according to study inclusion criteria. Preoperative nurses will email (emailing patients is part of normal practice) the participant information sheet to potentially eligible patients a minimum of 48 hours prior to their appointment. A short period between provision of study information and follow-up by the research team is justified in the context of potentially short surgical pathways in the study population.

During their appointment, the patient will be asked by the preoperative nurse if they are interested in participating in the study. If they are interested, the patient will be introduced to a researcher who will be present in the preoperative clinic. For those patients who are not interested in being involved in the study, we are interested in capturing the reasons why for research reporting and to inform the design of a future RCT. We will explain to these patients that they do not need to give a reason as they are free to decline to answer, but that it would be really helpful if they could explain their reason for declining involvement, as this will contribute to research reporting and future study design of this project.

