 - Exercise intensity: comparing the RPE reported by participants to the target RPE prescribed (i.e., RPE 5-10/10 is the target, so RPE 6/10 would be compliant but RPE 4/10 would be non-compliant). The proportion of aerobic and resistance sessions that are completed at the target intensity will be reported. It has been shown that an RPE score reported at the end of an exercise session is equivalent to the average RPE reported after each exercise (Day et al., 2004).

- Exercise type: after each session, participants will respond to the question: “how much of the session could you complete?” with options: all / most / some / none. If they select any option other than “all”, they will be asked to identify any exercises included in their session that they couldn’t complete from a list. Any sessions where ≥ 1 exercise was not completed will be deemed non-compliant to the type of exercise prescribed. The proportion of sessions where all exercises are completed will be reported.
- Duration: after each session, participants will respond to the question: “how much of the session could you complete?” with options: all / most / some / none. If they select any option other than “all”, they will be asked to identify any exercises included in their session that they couldn’t complete from a list. If they do not select any specific exercise, then we infer that participants were unable to perform the exercises for the required duration. Any sessions where most / some / none is reported with no specific exercise identified will be deemed non-compliant to duration. The proportion of sessions where exercises were performed for the target duration will be reported.
- Retention: the proportion of patients that enrol into the study who complete follow-up measurements
- Safety: the incidence and severity of adverse events reported during the weekly check-in session with a member of the research team, and via a free-text response box after each exercise session to be completed if the participant indicates that they could not perform all exercises.

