- Acceptability (week 7 only): collected via a survey integrated within PreActiv’s prehabilitation platform containing a combination of Likert scale and open-response questions about participant experiences of using PreActiv’s digital prehabilitation (Appendix 2). Responses to the survey will be fully anonymised, meaning responses cannot be attributed to the participant by name or study ID. Additional feedback will be obtained from comments submitted by participants to the community forum throughout the intervention.

Secondary outcome measurements will be conducted at the University of Bath during week 0 (pre-intervention) and week 7 (post-intervention), with each visit lasting 1-hour:

Participant characteristics

- Baseline characteristics (week 0 only): age, sex, ethnicity, surgery type, comorbidities, medications, mobility, transport to hospital visits (Appendix 3).

Physical assessments

- Resting blood pressure and heart rate will be measured using an automated sphygmomanometer after 15 minutes of seated rest.
- Cardiorespiratory fitness: Cardiopulmonary exercise tests (CPET) will be performed using a ramp-incremental protocol on a cycle ergometer. Body mass, height, and resting blood pressure will be measured prior to commencing exercise. After a 3-minute low-intensity warm-up, participants will be instructed to maintain a consistent cadence of 50-70 rpm during a ramp protocol whereby the resistance against the pedals increases incrementally over time. The rate of the incremental ramp protocol will range from 5-30 watts/minute, based on participant’s ability, with the aim of achieving maximal exertion within 8-12 minutes. Participants will be encouraged to exercise to maximal exertion. Heart rate, blood pressure, oxygen saturation, and rating of

perceived exertion (RPE) rated from 0-10 will be monitored throughout. A 5-minute low intensity cool-down will be completed after the ramp protocol with monitoring of heart rate and blood pressure recovery. Measurements of $VO_{2\text{PEAK}}$ and ventilatory threshold will be derived from CPETs.

- Functional fitness: 1-minute sit-to-stand test (for participants able to transition from seated to standing unsupported) or 1-minute seated push-up test (for participants unable, or requiring support, to transition from seated to standing).

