
When asked about attending the University of Bath for the measurement visit, patients reported that: “it is quite intimidating for people who haven’t been there”.
	
We need to use equipment at the University of Bath for the study measurements, and as such, it was not possible to change the venue. We will provide participants with a detailed map and directions to the car park. The researcher will meet them in the car park and walk with them to the laboratory. Patients will also be given a contact number for the researcher if they have any issues. This approach has been successful in previous research studies.

When asked about the benefits they would be hoping for if they took part in the intervention, patients reported that: “seeing fitness results improving during the programme” and “noticing an impact after surgery” were important to them.
	
We explained to patients that measuring postoperative outcomes was outside the scope of this feasibility study, but that such measures would be included in a future study. The platform involves repeated assessments of fitness every two weeks, where participants can see their results progress in their user profile.

When asked about incentives for taking part, patients reported: “a certificate of results would give a sense of achievement” and “money is not needed”.
	
We will provide participants with a certificate of their progress during the intervention, plus a report of results from health, fitness, and wellbeing assessments performed at the University of Bath. We will provide money to cover the costs associated with taking part in the study.

When asked for their feedback on the participant information sheet, patients reported that it looked professional and was easy to understand, but that it was quite long and a summary would be helpful. Patient’s proposed that they could talk to the researcher for more details.
	
We have included a two-page executive summary within the participant information sheet, which contains the most important information for patients to decide whether to take part. The researcher will talk through the details of the participant information sheet during the screening and consent visit.

7. Benefits of participating

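### Week-7 IPAQ, EQ-5D-5L and HADS are planned only at the University visit that includes the maximal exercise test, so non-attenders give no follow-up self-report data; retention does not say which measurements count

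*Combined protocol and SAP*

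**What the plan says.** Section 5d (Measurements) sets the place and time of the secondary outcomes: "Secondary outcome measurements will be conducted at the University of Bath during week 0 (pre-intervention) and week 7 (post-intervention". The list beneath covers resting blood pressure and heart rate, a ramp cycle test to maximal exertion, a one-minute functional test, and three instruments the participant fills in: IPAQ short form, EQ-5D-5L and HADS. No postal, telephone, email or in-platform route is given for these three.

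Other outcomes do not depend on the visit. The acceptability survey, also due in week 7, is completed on the platform. Adherence comes from platform records, compliance from in-platform responses, and safety from weekly check-ins and free text after sessions.

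The feasibility list in the same section defines "Retention: the proportion of patients that enrol into the study who complete follow-up measurements". It does not say which measurements, or how many, must be completed. Section 5a makes retention one of "two key outcome measures - adherence and retention" that carry the traffic-light table, whose row reads "Retention 0-50% 51-74% 75-100" (per cent). Section 5e plans mainly descriptive analysis with effect sizes for pre-to-post change, and does not mention missing follow-up.

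**The concern.** A questionnaire needs no laboratory. By tying IPAQ, EQ-5D-5L and HADS to the exercise-test visit, the plan makes their follow-up depend on a journey and on attending a demanding appointment shortly before surgery. Every week-7 non-attender then drops out of the pre-post comparison on activity, quality of life and mood, although many might have answered by email or telephone. Attenders may differ from non-attenders, so the effect sizes carried forward to the larger study could describe a selected group.

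The second stake is the progression decision. Because the definition names no measurement, the same participants could be counted as retained or not, depending on a rule chosen later. Choosing it after the data are seen would defeat the purpose of a predefined criterion.

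**Working it through.** **Inputs from the plan (section 5a).** Size: "recruitment will cease once $N = 34$ participants have provided written informed consent". Test: red limit 50%, green limit 75%, "with 90% power and one-sided alpha of 0.05".

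**Reproducing the plan's own figure.** One-sample proportion, one-sided:

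n = [(1.645·√(0.50·0.50) + 1.282·√(0.75·0.25)) / 0.25]² = [(0.8224 + 0.5549) / 0.25]² = 30.4.

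With continuity correction: (30.35/4)·[1 + √(1 + 2/(30.35·0.25))]² = 34.2. This matches the stated 34 (approximate power 89.8%). The exact binomial rule at 34 rejects 50% with 23 or more retained (alpha 0.029, power 0.881). The sample size is not in dispute.

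**Where the green line falls.** 0.75 × 34 = 25.5, so green needs 26. 26/34 = 76.5%; 25/34 = 73.5%, which is not green. At most 34 − 26 = 8 can be lost.

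**Size of the questionnaire loss if retention means attendance.**
- Lowest green result: 8/34 = 23.5% have no week-7 IPAQ, EQ-5D-5L or HADS.
- Lowest amber result, 18/34 = 52.9%: 16/34 = 47.1% have none.

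These follow from the plan's own bands. They show what the bands permit and do not forecast attendance.

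**How far the retention definition can move the traffic light.** The documents give no attendance rate, so both quantities here are assumptions: a = share attending week 7; s = share of non-attenders who would return questionnaires remotely and be counted as retained. Then q = a + (1 − a)·s, and P(green) = P(X ≥ 26) with X ~ Binomial(34, q).

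| a | s = 0 | s = 0.25 | s = 0.50 |
|---|---|---|---|
| 0.65 | 0.11 | 0.45 | 0.87 |
| 0.70 | 0.27 | 0.65 | 0.94 |
| 0.75 | 0.51 | 0.83 | 0.98 |

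Example: a = 0.70 and s = 0.50 give q = 0.70 + 0.30 × 0.50 = 0.85, and P(green) rises from 0.27 to 0.94.

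**What a remote route would recover.** In the same example, the expected number with week-7 questionnaires rises from 34 × 0.70 = 23.8 to 34 × 0.85 = 28.9, about 5 more. Each is a usable pair only if the participant also has baseline data.

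The table shows two things. The rule must be fixed in advance, and counting remote returns as retained would make the go decision much easier to reach.

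**The case against.** The strongest reply is that the plan is silent rather than wrong, and that the outcomes at risk are secondary ones in a pilot that says it is underpowered for them. Much of this stands.

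- A reader might infer that every week-7 outcome hangs on the visit. It does not: acceptability is collected on the platform, and adherence, compliance and safety need no attendance.
- A reader might infer that people who stop the programme lose their follow-up. No text bars them from week 7. Nor does any text make the exercise test a condition of completing the questionnaires or of being counted as retained.
- Two statements look like evidence of heavy week-7 loss but are weak support. In section 6 a patient said of the venue that "it is quite intimidating for people who" had not been there before; by week 7, anyone measured at baseline has been. The section 1 barrier, "lack of time and difficulty travelling to facilities on a regular basis", concerns repeated prehabilitation sessions, not two research visits. Sections 6 and 7 also offer directions, an escort from the car park, a contact number and travel reimbursement.
- Retention need not capture engagement as well, because adherence has its own row in the progression table.
- Willingness to return for fitness testing is itself useful feasibility information, since the larger study is meant to examine preoperative fitness.

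Two points survive. The venue is kept because of the equipment there, and questionnaires need none; the support offered helps those who come and does nothing for those who do not. And nothing in the plan fills the gap in the retention definition.

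**Conclusion.** The point holds in a limited form. As written, the plan loses all measured week-7 secondary outcomes for each non-attender, including three self-reports that could be obtained without a visit. That is up to 8 of 34 (23.5%) even at a green result, if retention is counted by attendance. The reported effect sizes would then rest on attenders alone. It is tempting to say that this flatters the intervention, but the documents do not show how non-attenders would differ, so the direction is unknown.

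Separately, the retention criterion is not fully defined, and the definition can change the traffic light. The probabilities above rest on assumed attendance and response rates. They show sensitivity to the rule, not a likely result. The sample size stands. This is a change the sponsor should make; it does not invalidate the design.

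**What to change.** 1. In week 7, offer IPAQ, EQ-5D-5L and HADS by email, post or telephone to every participant who does not attend and has not withdrawn consent, including those who stopped the programme. Record the completion setting and flag it in the analysis.
2. Before recruitment, state which measurements count as retention. Keep the row read against the progression table on attendance at the week-7 visit, so that remote returns do not loosen the go criterion.
3. Report two further lines over all 34 consented: any week-7 measurement, and exercise-test completion, each with reasons for non-completion.

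The anonymous acceptability survey cannot serve as the fallback, because its responses cannot be linked to a participant.

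Cost: a short amendment and a few extra contacts by existing researchers, with no new instrument and no change to N. A few questionnaires will be completed in a different setting from baseline, which the flag makes visible.

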- **Compliance:** If participants report an RPE <5 for aerobic and/or resistance exercise on two occasions, they will be telephoned by a researcher to assess why they have scored their RPE <5. If poor technique or lack of understanding is causing RPE <5, education on the importance of intensity and how to achieve higher intensities will be provided. If technique/understanding are not the issue, and the programme is too easy, the course would be adapted manually (in the future, the adaptation of the course would be partially automated).

Non-exercise intervention

General advice and information on services relating to alcohol consumption, smoking, and nutrition will be provided in the PreActiv eBook. Specific instruction or advice on alcohol, smoking, and nutrition is beyond the scope of this iteration of the PreActiv digital platform but will be included in subsequent versions.

A community forum will be provided within the PreActiv digital platform, which will allow people undergoing similar surgeries to share experiences, discuss queries, and seek support from peers. Participants will have access to the community forum throughout their prehabilitation programme, and for one month post-surgery, to allow participants to share comments about their surgery and recovery experience. All comments made in the community forum will be archived for later analysis in order to further refine and evaluate PreActiv's digital prehabilitation.

There will be a check-in session on a Monday with a member of the research team via the community forum so users can access health professional support. This support is included in the implementation plan and is part of the intervention.

d. Measurements

Primary outcome measurements will be collected throughout the study (week 0-7).

Feasibility

- Recruitment rate: the proportion of patients invited that provide written informed consent
- Uptake: the proportion of patients invited that are willing to be screened for eligibility
- Screen-pass rate: the proportion of willing patients that pass screening for eligibility
- Adherence: the proportion of exercise sessions offered that are attended, assessed based on the number of sessions completed on the PreActiv platform (note: subsequent exercise sessions only become available to participants once they have watched the previous video).
- Compliance: the proportion of exercise sessions that are completed as prescribed:

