 - 1-minute testing protocols have been selected to increase the emphasis on measuring endurance rather than muscular strength, due to the associations between cardiorespiratory fitness and surgical outcomes. The 1-minute sit-to-stand test has been shown to induce similar cardiorespiratory responses as cardiopulmonary exercise testing in COPD patients (Gephine et al., 2020), and has been implemented in prehabilitation trials (Bradley et al., 2023). The 1-minute seated push-up test is a relatively novel assessment, and has been shown to correlate with other functional fitness measures (Chokphukiao et al., 2023, Poncumphak et al., 2023).
- Self-report physical activity: Participants will complete the IPAQ short-form questionnaire to self-report days per week and minutes per day of vigorous intensity physical activity, moderate intensity physical activity, walking, and sitting. 'MET-hours' (MET = metabolic equivalent of task) per week will be calculated. This information will be compared to the WHO guidelines on physical activity and sedentary behaviour.

Psychological assessments

- Quality of life: Participants will complete the EQ-5D-5L to provide insights into mobility, self-care, usual activities, pain/discomfort, and anxiety/depression.
- Mood: Participants will complete the Hospital Anxiety and Depression Score

Economic & environmental

- Cost per patient to deliver PreActiv's digital prehabilitation, with comparison to published costs for face-to-face and telemedicine prehabilitation programmes
- Environmental impact avoided by performing prehabilitation at home via PreActiv's digital prehabilitation compared to the estimated hypothetical emissions associated with participants travelling to the hospital three times per week for six weeks for face-to-face prehabilitation. Publicly-available carbon emissions data will be used for calculations.

e. Data analyses

The primary aim of this study is to test feasibility of the PreActiv's digital prehabilitation. Feasibility will be assessed by reporting proportions and comparing to predefined progression criteria (for adherence and retention). This pilot study is not adequately-powered to investigate the statistical significance of pre- to post-intervention changes to secondary outcome measures. As such, data analyses will be predominantly descriptive. Effect sizes will be reported to convey the magnitude of pre- to post-intervention changes to secondary outcomes.

6. Patient and public involvement (PPI)

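### The 5% and 90% used to justify N = 34 belong to a test that the progression rule in section 5e does not apply

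*Combined protocol and SAP*

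**What the plan says.** Section 5a says that the sample size serves the primary aim "to determine whether progression to a full-scale study is indicated, according to predefined progression criteria". For both adherence and retention it sets red at 0-50%, amber at 51-74% and green at 75-100%. It then describes the calculation as "aiming to test the hypothesis that feasibility outcomes will not fall within the red zone", on the expectation of being in green, and concludes: "with 90% power and one-sided alpha of 0.05, we need to consent $N = 34$ participants".

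Section 5d defines the two outcomes. Retention is counted per person: "Retention: the proportion of patients that enrol into the study who complete follow-up measurements". Adherence is counted per session: "the proportion of exercise sessions offered that are attended, assessed based on the number of sessions completed on the PreActiv platform".

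Section 5e holds the whole analysis rule for feasibility: "Feasibility will be assessed by reporting proportions and comparing to predefined progression criteria (for adherence and retention". Neither 5d nor 5e gives a test, a critical count or a confidence bound for adherence or retention, or says how the test in 5a bears on the zone. The remark in 5e that analyses will be mainly descriptive follows from the lack of power for the secondary outcomes.

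**The concern.** A one-sided 5% test of 50% and a comparison of an observed percentage with a 50% limit are different rules. The first needs a result far enough above 50% to exclude 50%. The second needs only a result above 50%. Section 5a quotes the error rates of the first, and section 5e applies the second.

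What is at stake is how an amber result may be described. A reader of 5a would expect a pilot that avoids red to have ruled out a true rate of 50% with 5% error. Under 5e a result in the lower part of amber carries no such assurance, and nothing in the planned report would show this.

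**Working it through.** **Inputs.** From section 5a: p0 = 0.50 (top of red), p1 = 0.75 (bottom of green), one-sided alpha 0.05, power 0.90, N = 34. From section 5d: retention is a proportion of patients. Assumption: all 34 consented patients count as enrolled, so retention is binomial with n = 34.

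**1. The plan's own figure.** With d = 0.25, z(0.95) = 1.645 and z(0.90) = 1.282:

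- Normal approximation: m = (1.645·√0.25 + 1.282·√0.1875)² / 0.25² = 30.35.
- With continuity correction: m/4 · (1 + √(1 + 2/(m·d)))² = 34.24. The corresponding power at n = 34 is 89.8%.

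The stated N = 34 and 90% are therefore consistent with their inputs to within rounding.

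**2. The rule in 5e on the retention counts.** 17/34 = 50.0% is red, 18/34 = 52.9% to 25/34 = 73.5% is amber, and 26/34 = 76.5% or more is green. With X ~ Bin(34, p):

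| True retention | Leaves red, P(X ≥ 18) | Green, P(X ≥ 26) |
|---|---|---|
| 40% | 8.7% | below 0.02% |
| 45% | 22.4% | 0.02% |
| 50% | 43.2% | 0.15% |
| 75% | 99.85% | 51.3% |

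At the boundary the rule has 43.2% where 5a states 5%, and at 75% it has 99.85% where 5a states 90%.

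**3. The test in 5a on the same counts.** The plan does not name the test, so two forms are shown.

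| Form | Excludes 50% from | Why | Exact size at 50% | Power at 75% |
|---|---|---|---|---|
| Exact binomial | 23/34 (67.6%) | p = 0.029; 22/34 gives p = 0.061 | 2.9% | 88.1% |
| Score, uncorrected | 22/34 (64.7%) | z = 1.71; 21/34 gives z = 1.37 | 6.1% | 93.9% |

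The exact one-sided 95% lower bound is 49.2% at 22/34 and 52.2% at 23/34. Results of 18 to 21 of 34 are amber although neither form excludes 50%, and 22/34 depends on the form chosen.

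**4. How often this arises.** P(18 ≤ X ≤ 22) is 11.8% at a true 75% and 49.9% at a true 65%.

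**5. Adherence.** Sessions are clustered within people, so the binomial figures do not carry over, and the documents give no between-participant variance. Purely for scale, assume that the per-participant proportions have an SD of 0.20 to 0.40 in 34 people. A one-sided 95% t-bound then excludes 50% only from a mean of 0.5 + 1.692·SD/√34, which is 55.8% to 61.6%. Amber starts at 51%.

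**The case against.** The strongest reply is that the plan does state its decision rule. The zones are fixed percentages, 5e compares observed proportions with them, and no other cut-off appears anywhere. This is right. A reader might infer that the progression rule is ambiguous, but the documents do not support that; what is missing is the link between the rule and the error rates quoted for it.

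Second, a large chance of leaving red at exactly 50% is a property of any cut-off placed on the estimate. It falls to 8.7% at 40% and 2.4% at 35%. This also stands: 43.2% is the worst case within red. Nor does leaving red mean proceeding. Nearly all of that probability is amber, which the plan labels as amend. A reader might infer a large risk of a false go; the 0.15% chance of green at a true 50% rules that out.

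Third, a reader might take the 88.1% as proof that the pilot is too small. That figure depends on choosing an exact test, which the plan does not name, and it reflects the discreteness of the binomial: the same test has 90.1% power at 33 patients. It gives no reason to change N.

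Fourth, 5a rests on a published sizing method that is not reproduced. Whether that method contains a decision rule cannot be judged from the documents. It can be said only that the protocol states none.

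What remains is that 5a claims 5% and 90%, and the rule written in 5e has neither.

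**Conclusion.** The point holds as a mismatch between the justification in 5a and the rule in 5e. For retention, that rule leaves red with probability 43.2% at a true 50% and 99.85% at a true 75%, against the stated 5% and 90%. A 5% test would exclude 50% only from about 22 or 23 of 34, so results of 18 to 21 (or 22) are amber without having excluded the red limit.

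The figures assume that all 34 consented patients are in the retention denominator, and they are per criterion. For adherence the same mismatch exists, but its size cannot be computed from the documents. The consequence is confined to the stop/amend boundary and to what is claimed for an amber result. Minor to moderate.

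**What to change.** In section 5e, keep the zones on the observed proportion and add text such as:

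> The zone for each criterion is set by its observed proportion. Beside it we report a one-sided 95% lower bound and whether 50% is excluded; this does not change the zone. For retention the bound is exact, and with 34 enrolled 50% is excluded from 23/34. For adherence the bound is t-based, on the mean of the per-participant proportions, because sessions are clustered within people.

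An amber retention result of 18 to 22 of 34 would then not be reported as having ruled out the red zone.

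In section 5a, say that the 5% and 90% refer to this test and not to the zone rule, for each criterion separately, and give the retention size and power of the test chosen (2.9% and 88.1% if exact). The alternative is to say that they were used for sizing only and to print the probabilities in the first table above.

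The cost is wording in two sections. No extra data are needed, N stays at 34, and no zone changes. The visible effect is that the results counted in step 4 (11.8% of trials at a true retention of 75%, 49.9% at 65%) would carry the statement that 50% is not excluded.

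A separate minor clarification can be made at the same time. Section 5c implies 3 × 6 = 18 planned sessions, but 5d notes that "subsequent exercise sessions only become available to participants once they have watched the previous video", so the plan should say whether sessions offered means planned or unlocked sessions.
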